### **3.4 Protocol deviations**

Important protocol deviations are deviations from the protocol which could potentially have a meaningful impact on study conduct or on the primary efficacy outcome for an individual subject. The criteria for identifying important protocol deviations will be defined within the specification of Protocol Deviations document. Important protocol deviations will be reviewed as part of the ongoing data cleaning process and all important deviations will be identified and documented prior to unblinding to confirm exclusion from analysis sets.

### **3.5 Analysis sets**

#### **3.5.1 Enrolled Set**

The Enrolled Set (ES) will consist of all subjects who have given informed consent.

#### **3.5.2 Randomized Set**

The Randomized Set (RS) will consist of all subjects randomized into the study.

#### **3.5.3 Safety Set**

The Safety Set (SS) will consist of all subjects in the RS who have received at least one dose of study medication.

#### **3.5.4 Full Analysis Set**

The Full Analysis Set (FAS) will consist of all subjects in the RS who have received at least 1 dose of study medication.

#### **3.5.5 Per Protocol Set**

The Per Protocol Set (PPS) will consist of subjects in the FAS without any important protocol deviations that may influence the validity of the primary efficacy data. Treatment compliance as defined in Section 7 may also be utilized. Important protocol deviations will be predefined and evaluated at the DEM prior to study unblinding at the Week 52 interim database lock. Protocol deviations occurring after Week 52 (for example, for subjects continuing in the SFE period) will not be considered for PPS impact as they occurred after assessment of the primary variable was performed.

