## **2.2 Study variables**

### **2.2.1 Efficacy variables**

#### **2.2.1.1 Primary efficacy variable**

- ASDAS-MI response at Week 52

For Canada (and any other country where applicable or where requested by Regulatory Authorities), the primary efficacy variable is:

- Assessment of SpondyloArthritis international Society 40% response criteria (ASAS40) response at Week 12

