## 8 EFFICACY ANALYSES

All efficacy analyses of the double-blind 52-week treatment period will be performed using the FAS. The PPS and Randomized Set will be used for a sensitivity analysis on the primary endpoint only (using the composite endpoint analysis). The SFE-FAS will be used for analysis of efficacy data at the Week 156/SFE-WD visit.

The statistical analysis of the primary efficacy variable and selected secondary efficacy variables will account for multiplicity by using a fixed sequence testing procedure. The predefined order of hypotheses testing, each at a 2-sided 0.05 significance level for the comparison between CZP 200mg Q2W and placebo, will be performed in the sequence shown below. After the first test, each subsequent test is performed only if the previous test is significant in favor of CZP at the 2-sided 0.05 level. Note that the first test relates to the primary efficacy variable while the others provide the sequential testing for selected secondary efficacy variables:

Primary:

1. ASDAS-MI response at Week 52 (Composite endpoint analysis)

Secondary:

2. ASAS40 response at Week 12 (Composite endpoint analysis)
3. Change from Baseline in BASDAI at Week 12 (Reference based multiple imputation analysis)
4. Change from Baseline in BASFI at Week 12 (Reference based multiple imputation analysis)
5. ASAS40 response at Week 52 (Composite endpoint analysis)
6. Change from Baseline in BASDAI at Week 52 (Reference based multiple imputation analysis)
7. Change from Baseline in BASFI at Week 52 (Reference based multiple imputation analysis)
8. Change from Baseline in SI joint SPARCC score at Week 12 (Reference based multiple imputation analysis)
9. Change from Baseline in ASQoL at Week 52 (Reference based multiple imputation analysis)

10. Change from Baseline in nocturnal spinal pain (NRS) at Week 52 (Reference based multiple imputation analysis)

11. Number of subjects with AU or new AU flares through Week 52

Hierarchical testing of efficacy variables for Canada (and any other country where applicable or where requested by Regulatory Authorities):

Primary:

1. ASAS40 response at Week 12 (Composite endpoint analysis)

Secondary:

2. ASDAS-MI response at Week 52 (Composite endpoint analysis)

3. Change from Baseline in BASDAI at Week 12 (Reference based multiple imputation analysis)

4. Change from Baseline in BASFI at Week 12 (Reference based multiple imputation analysis)

5. ASAS40 response at Week 52 (Composite endpoint analysis)

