### 8.1.3 Supportive and sensitivity analyses of the primary efficacy variable

As described in [Section 6.3](#) of the protocol, subjects who discontinue study treatment will not necessarily be withdrawn from the study. In an attempt to minimize missing data, efforts will be made to continue to collect safety and efficacy data on these subjects through study completion. In order to assess the impact of various missing data assumptions on the analysis, four sensitivity analyses of the primary efficacy variable will be performed as described in [Section 4.2.1](#). Further details of these analyses are provided in this section. The odds ratios  $\pm$  95% CI's for the primary analyses and sensitivity analyses will be presented on the same graph to allow visual comparison of the robustness of the results. In addition, a summary of the missing data pattern will be provided.

For Canada (and any other country where applicable or where requested by Regulatory Authorities), the primary efficacy variable measurement is the ASAS40 response at Week 12. Analysis of the ASAS40 response at Week 12 will be performed as described above for

ASDAS-MI response at Week 52 (including all sensitivity and subgroup analyses). Similar to the ASADAS-MI efficacy endpoint, the primary analysis of ASAS40 will be treated as a composite endpoint when it is analyzed. Specifically, subjects will need to: 1) achieve the relevant response (ASAS40); and 2) remain in the study and on their randomized double-blind study treatment through Week 12.

In addition to the above analyses, subgroup summaries using descriptive statistics, estimates and confidence intervals only for the primary efficacy variable by age, gender, race, symptom duration, tobacco use, HLA-B27 genotype, region, prior anti-TNF exposure, Baseline SPARCC score ( $<5$ ,  $\geq 5$ ), subjects with/without relevant changes to background medication, and MRI/CRP classification (MRI+/CRP+; MRI+/CRP-; MRI-/CRP+) will be performed.

The logistic regression analyses of the composite endpoint for ASDAS-MI responder rates at Week 52 (as described in [Section 8.1.2](#)) will also be repeated using the PPS and the Randomized Set. In addition, the primary analysis will be repeated where ASDAS-MI includes the criteria ASDAS reduction (improvement) of  $\geq 2.0$  relative to Baseline only.

### 8.1.3.1 Including observed data at Week 52

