### **8.2.2.1 Primary analysis of categorical secondary efficacy variables**

The ASAS40 response at Week 12 and Week 52 are responder secondary efficacy variables. For Canada and any other country where applicable or where requested by Regulatory Authorities, the ASAS40 response at Week 12 is the primary efficacy variable; the ASAS40 response at Week 52 and the ASDAS-MI response at Week 52 are secondary efficacy variables. Hence the primary and sensitivity efficacy analysis on ASDAS-MI at Week 52 will be repeated for ASAS40 at Week 12.

As a responder variable, ASAS40 will be analyzed using logistic regression in the same manner as for the primary analysis described in [Section 8.1.2](#). As with the primary efficacy variable, the ASAS40 will be treated as a composite endpoint when it is analyzed. Specifically, subjects will need to 1) achieve the relevant response (ASAS40) and 2) remain in the study and on their randomized double-blind study treatment through the time point being analyzed (Week 12 or Week 52).

Relevant changes to background medication will also be analyzed using the same composite endpoint logistic regression model described for the primary variable described in [Section 8.1.2](#).

The number of subjects with new onset post-Baseline AU or new AU flares through Week 52 is a categorical secondary efficacy endpoint for all regions. Subjects will be classified as having post-Baseline Uveitis: a TEAE of Uveitis, a new diagnosis of Uveitis or a flare of uveitis at any visit post-Baseline which is on or before the Week 52 visit. All subjects without evidence of uveitis events, new diagnosis or flares will be considered not to have post-Baseline Uveitis. As a dichotomous outcome variable, treatment groups will be compared for differences using logistic regression including treatment, region and MRI/CRP classification as explanatory variables. Subjects with no evidence of new AU flares will be considered as having no flare.

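### The SAP's only Per Protocol Set is cut at Week 52, but cross-references appear to apply it to ASAS40 at Week 12 as well, so events after that outcome could exclude subjects

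*SAP*

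**What the plan says.** Section 3.5.5 of the SAP defines a single PPS: members of the Full Analysis Set (FAS) "without any important protocol deviations that may influence the validity of the primary efficacy data". It adds an optional criterion, "Treatment compliance as defined in Section 7 may also be utilized", and a time limit, "Protocol deviations occurring after Week 52 (for example, for subjects continuing in the SFE period) will not be considered for PPS impact", justified "as they occurred after assessment of the primary variable was performed". No other per protocol set appears in Section 3.5.

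Section 2.2.1.1 gives ASDAS-MI at Week 52 as the primary variable. For Canada, and other countries where applicable or requested, it is instead "Assessment of SpondyloArthritis international Society 40% response criteria (ASAS40) response at Week 12".

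On use of the set, Section 8 says: "The PPS and Randomized Set will be used for a sensitivity analysis on the primary endpoint only (using the composite endpoint analysis". Section 8.1.3 extends the ASDAS-MI analyses to ASAS40 at Week 12, "including all sensitivity and subgroup analyses". Section 8.2.2.1 says much the same: "Hence the primary and sensitivity efficacy analysis on ASDAS-MI at Week 52 will be repeated for ASAS40 at Week 12". The closing paragraph of Section 8.1.3, which orders the PPS rerun of the logistic regression, names only ASDAS-MI at Week 52.

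**The concern.** The reason given for the Week 52 limit is that a deviation after the outcome was assessed cannot affect it. For ASAS40 at Week 12, the same reasoning puts the limit at Week 12. The ASAS40 composite already follows that logic, since Section 8.1.3 requires a subject to stay on double-blind treatment only through Week 12. The PPS does not follow it.

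If the PPS is used for ASAS40 at Week 12 as it stands, membership depends on up to 40 weeks of conduct after the outcome. Later conduct can depend on response and on treatment arm, so the Week 12 per protocol comparison would be conditioned on post-outcome events. It could be distorted, and it would lose subjects whose Week 12 data are sound. At stake is a supportive check on a regional primary endpoint.

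**Working it through.** **Does the PPS reach ASAS40 at Week 12?** The route is by cross-reference only.

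- Section 8 assigns the PPS to a sensitivity analysis of the primary endpoint, and Section 4.6 also calls the PPS analysis a planned sensitivity analysis.
- Section 2.2.1.1 makes ASAS40 at Week 12 the primary variable for some authorities.
- Sections 8.1.3 and 8.2.2.1 carry the sensitivity analyses over to it.
- Section 8.1.3 describes the carried-over analyses as those set out above. The subgroup paragraph stands below that sentence and is nevertheless expressly included, so position in the text does not exclude the PPS paragraph, which also stands below.

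Taken together, this is the more natural reading, but it is not an explicit instruction.

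**Share of scheduled dosing after the Week 12 outcome** (Section 7: two syringes at Weeks 0, 2 and 4, one at every other visit, 14-day interval, last dose at Week 50).

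- Dosing visits: 50/2 + 1 = 26, and maximum duration 50 × 7 = 350 days. Both match the figures in Section 7.
- Syringes: 3 × 2 + 23 × 1 = 29.
- Before Week 12 (Weeks 0, 2, 4, 6, 8, 10): 6 visits and 3 × 2 + 3 × 1 = 9 syringes.
- At or after Week 12: 26 − 6 = 20 visits, 20/26 = 77%; 29 − 9 = 20 syringes, 20/29 = 69%.

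**What late non-compliance alone can do.** Take a subject dosed exactly on schedule through Week 10 who misses 6 of the later 20 doses but takes the Week 50 dose.

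- Syringe ratio: (29 − 6)/29 = 23/29 = 0.79.
- Injection-day ratio, with 14 days charged per missing date: (350 − 6 × 14)/350 = 266/350 = 0.76.

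Both fall below 0.80, with every dose before Week 12 given on time. Treating 0.80 as a PPS threshold is an assumption: Section 7 uses it only as a summary category, and the SAP sets no threshold for the PPS.

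**Possible loss of subjects.** The SAP gives no rate. If 5% to 30% of the 300 planned subjects were excluded only for events between Weeks 12 and 52, the loss would be 0.05 × 300 = 15 to 0.30 × 300 = 90.

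**Possible movement of the estimate.** All inputs are assumed. The rates are borrowed from the ASDAS-MI Week 52 planning values in Section 2.4, because no ASAS40 Week 12 rate is given.

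- All subjects: CZP 60/150, placebo 30/150. Odds ratio = (60/90)/(30/120) = 2.67.
- Remove 15 placebo non-responders: placebo 30/135 = 22.2% instead of 20.0%. Odds ratio = (60/90)/(30/105) = 2.33.
- Remove 15 CZP non-responders instead: CZP 60/135 = 44.4% instead of 40.0%. Odds ratio = (60/75)/(30/120) = 3.20.

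The estimate moves either way depending on which arm loses subjects, so the documents fix no direction.

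**The case against.** Four objections carry weight.

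**Scope.** The PPS may never have been meant for ASAS40. Section 8.1.3 speaks of four sensitivity analyses, Section 4.2.1 lists them as missing-data methods and repeats those for ASAS40 at Week 12, and Section 8.2.3 lists the ASAS40 sensitivity analyses without the PPS. This stands as far as it goes: a reader might infer that the SAP definitely plans a Week 12 PPS analysis, and it does not say so outright. It still has to say which is meant, because Sections 4.6 and 8 class the PPS analysis as a sensitivity analysis.

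**Certainty of exclusion.** A reader might infer that a deviation at, say, Week 30 necessarily removes a subject. It does not. A deviation must be judged able to affect the validity of the primary efficacy data, the criteria sit in a separate document (Section 3.4), and compliance is optional. A judgement made for the Week 12 variable could ignore a Week 30 event. But one set with one membership list serves both variables, and a deviation that matters for Week 52 would carry over to Week 12.

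**Mechanism.** A reader might infer that late exclusions selectively remove placebo non-responders. The documents do not support that. Background medication may be adjusted (Section 11.2), treatment may be stopped for non-response (Section 8.1.3.2), and subjects may switch to open-label CZP or other treatment (Section 2.3.1), so much of what non-responders do later is allowed by design. Expected syringes are counted only up to the last dose before a switch, so switching does not lower the syringe ratio. The injection-day sum is less clear, since Section 7 runs it over all 26 visits.

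**Size.** It is also tempting to turn 77% of dosing visits into three quarters of exclusions. That would need deviations spread evenly over time and would leave out eligibility failures. The SAP gives no basis for the first, and Section 4.8 shows that eligibility failures do exclude subjects.

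**Conclusion.** The point holds as a minor defect. The SAP has one PPS with a Week 52 limit, and the reason it gives for that limit would require a Week 12 limit for the regional primary variable. On the more natural reading of the cross-references, subjects can be excluded from a Week 12 per protocol analysis for events that cannot have influenced the outcome. Most of the scheduled dosing on which compliance could be judged (20 of 26 visits, 20 of 29 syringes) lies at or after Week 12.

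This rests on two conditions: that the PPS analysis does extend to ASAS40 at Week 12, and that some deviations or compliance failures between Weeks 12 and 52 lead to exclusion. The number of subjects and the direction of any bias cannot be determined from the SAP. The FAS composite analysis, the testing sequence and type I error are unaffected.

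**What to change.** Choose one of two edits.

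1. Define a Week 12 PPS for ASAS40 at Week 12 that counts only eligibility deviations, plus deviations and compliance up to the Week 12 assessment. Keep the existing PPS for ASDAS-MI at Week 52. Derive the new flag mechanically from dated deviation and dosing records, using the criteria already agreed, so that no fresh judgement on individual subjects is needed.
2. State in Sections 3.5.5, 8 and 8.1.3 that the PPS analysis applies to ASDAS-MI at Week 52 only.

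Timing affects the first option. Sections 2.2.1.3 and 8.1.1 refer to double-blind outputs already produced, and Section 4.3 releases treatment codes at the Week 52 lock. If that unblinding has passed, the Week 12 set should be labelled as added afterwards.

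The first option costs one derived flag, one rerun of the logistic regression and a short paragraph. The second costs a sentence in each place. Neither needs new data.

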#### **3.5.6 SFE Safety Set**

The SFE Safety Set (SFE-SS) will be defined as all subjects who continued into the SFE Period and who received at least 1 dose of CZP in the SFE Period. Safety data recorded during the SFE will be presented alongside the Week 52 analyses and hence it is not expected that this analysis set will be required.

### 3.5.7 SFE Full Analysis Set

The SFE Full Analysis Set (SFE-FAS) will be defined as all subjects in the FAS, who continued into the SFE Period and who received at least 1 dose of CZP in the SFE Period. This analysis set will be used to analyze efficacy data at Week 156/SFE-WD.

### 3.6 Treatment assignment and treatment groups

At Baseline, eligible subjects will be randomly assigned in a 1:1 ratio to the following double-blind study treatments:

- Placebo (PBO)
- CZP administered sc at the loading dose of CZP 400mg Q2W at Weeks 0, 2 and 4 followed by CZP 200mg Q2W (starting at Week 6)

For presentation purposes, the terms CZP 200mg Q2W and PBO will be used.

For disposition, demography, Baseline characteristics and protocol deviations, in addition to the CZP 200mg Q2W and PBO groups, an all subjects group (CZP 200mg and PBO combined) will be displayed.

In general, for by visit data collected during the open-label period, subjects will be presented according to the treatments received in the double-blind period (CZP 200mg Q2W and PBO). For the by visit data collected during the SFE period, subjects will be presented in a single CZP 200mg Q2W treatment group.

Concomitant medications will be summarized according to whether they were taken: during the double-blind period by CZP 200mg Q2W or PBO, or during the open-label period by PBO->OL CZP (subjects who were randomized to PBO and then received open-label CZP), CZP->OL CZP (subjects who were randomized to CZP and then received open-label CZP)- or by the OL-OT group. In addition, concomitant medications taken during any CZP medication period of the main study (Total CZP incl DB and OL) and all concomitant medications (All subjects, including OL-OT but excluding SFE) will also be summarized. See [Section 6.4](#) for more detail.

AEs will be assigned to periods based on whether they started during the double-blind, OL-CZP, OL-OT, or SFE periods. Data corresponding to the OL-OT group will not be summarized, but only presented in listings. AEs will be summarized as follows:

- Double-blind period by CZP 200mg Q2W or PBO,
- Open-label CZP period by PBO->OL CZP or CZP->OL CZP (as above),
- SFE period by OL CZP
- Total CZP incl DB and OL (includes randomized CZP 200mg Q2W and AEs starting in the open-label CZP period).
- Total CZP incl DB, OL, and SFE OL (includes randomized CZP 200mg Q2W, AEs starting in the open-label CZP period and AEs starting in the SFE period).

See [Section 11.2](#) for more detail.

If it is determined after unblinding that the subject received a treatment other than the one to which they were randomized, safety tables will still be based on the randomized treatment for the SS. However, additional safety tables based on the actual treatment received may also be prepared whereby all data taken on or after the 1st administration of CZP is summarized according to the CZP treatment group no matter which treatment they were randomized to. The efficacy analyses will strictly follow the intention to treat principle, and no correction for receiving incorrect treatment will be performed.

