Subjects who discontinue the double-blind study treatment and enter open-label treatment with CZP will be assessed 2 and 4 weeks after open-label CZP treatment has been initiated and every 12 weeks thereafter. Alternatively, subjects who discontinue the double-blind study treatment and receive other treatment (including biologics) will be assessed every 12 weeks after initiation of the open-label other treatment (OL-OT). In either alternative schedule, assessments should be conducted until as close as possible to Week 52 (within  $\pm 4$  weeks), where Week 52 is relative to

the original randomization at Week 0. Subjects will then be invited to the Week 52 assessment visit.

**Period 3** (Follow-up period) - All subjects not participating in the SFE period after Week 52, including those withdrawn from the study prematurely, will have a single Follow-up visit, 8 weeks after Week 52/WD visit (10 weeks after their last administration of study medication).

**SFE Period** - Week 52 to Week 156, open-label:

At the completion of the Week 52 visit assessment, subjects on double-blind study treatment may receive open-label CZP treatment for an additional 2 years. Subjects who withdrew from double-blind study treatment and transitioned to open-label CZP treatment are also eligible to participate in the SFE period after completing the Week 52 visit assessment. Subjects on OL-OT are not eligible to participate in the SFE period.

Eligible subjects are allowed to roll-over to the SFE-period up to 3 months after completion of the Week 52 assessments.

Starting at Week 64, all subjects are to visit the site approximately every 12 weeks ( $\pm 2$  weeks) for assessments. The last dosing visits will be at Week 154. The final study assessments are performed at Week 156/Safety Follow-up Extension-Early Withdrawal Visit (SFE-WD) ( $\pm 1$  week). However a  $\pm 4$  week window will be used in the analysis for the Week 156 timepoint. The expected day for Week 156 will be calculated assuming that the SFE period start was on Week 52, i.e. Week 156 will be expected to be  $(156-52) \times 7$  days after Week 52. For patients where the first dose after the Week 50 visit is before the SFE informed consent the width of the lower boundary of the Week 156 window will be increased further by the absolute number of days between the first dose after the Week 50 visit and the SFE informed consent date.

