### 3.3 Definition of Baseline values

Unless otherwise specified, the last valid measurement before study medication administration in the double-blind period will be used as the Baseline value. The same Baseline definition will be used for the open-label period and SFE period. For almost all variables, this will be the assessment made at the Baseline visit. However, for some variables (eg, demography) assessments are scheduled for the Screening visit only and not for the Baseline visit. In this case, the Screening value will be utilized as Baseline value. If a Baseline visit measurement is missing, and a Screening visit measurement is available, the Screening value will be utilized as Baseline. If a scheduled Baseline assessment is taken on the same day as first administration of study medication and no time is collected, it will be assumed to have been taken prior to study medication.

Baseline images, either spinal x-ray or MRI assessments, are required to evaluate study eligibility. Therefore, all Baseline images will be available prior to randomization into the study. SI joint x-rays should not be older than 12 months prior to Baseline and should be verified by central reading during the Screening period.

There will be an additional SFE Baseline presented in some tables. It is defined as the last value before the patient received SFE treatment (the first dose on or after SFE informed consent, for most patients this will be the Week 52 value).

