## **8.4 Analysis of other efficacy variables during SFE**

In order to assess long-term efficacy of CZP for subjects with nr-axSPA, the following summaries will be presented on the SFE-FAS:

- The number and percentage of subjects achieving response for all categorical variables collected at Week 156/SFE-WD (ASDAS-MI reduction of  $\geq 2.0$  or lowest ASDAS score possible, ASDAS-MI reduction of  $\geq 2.0$ , ASDAS-CII, ASAS40, ASAS20, ASAS partial remission, BASDAI 50 and SPARCC score  $< 2$ ). In addition, a 2-sided exact (Clopper-Pearson) 95% confidence interval for the percentage of subjects achieving response will be presented. As described in Section 4.2.3, the summary will include a composite endpoint analysis, observed case analysis at Week 156 and observed case analysis at Week 156/SFE-WD.
- Subgroup analysis of ASDAS-MI responders (reduction of  $\geq 2.0$  or lowest score possible) and ASAS40 responders by Age group, Gender, Symptom Duration, HLA-B27 Genotype and MRI/CRP classification (as defined in section 4.8) using the composite endpoint analysis described in Section 4.2.3 including 2-sided exact (Clopper-Pearson) 95% confidence intervals for the percentage of subjects achieving response.
- The number and percentage of subjects with ASDAS-ID, ASDAS-MD\*, ASDAS-HD, ASDAS-vHD at Week 156 (completers only) and at Week 156/SFE-WD  
\* ASDAS-MD is equivalent to ASDAS-LD. Whereas protocol amendment 5 uses ASDAS-LD throughout the SAP and Shells will continue to use ASDAS-MD in order to maintain consistency with the double-blind TFLs previously produced for this study.
- Summary statistics along with the changes from baseline for ASDAS, BASDAI (total score, individual Questions 1, 2, 3, 4 and morning stiffness [the average of Q5 and Q6 of the BASDAI]), BASFI, SI Joint SPARCC, PGADA, nocturnal spinal pain, total spinal pain, CRP and ASQoL, collected at Week 156/SFE-WD. As described in Section 4.2.3, observed data for completers only (at Week 156) in addition to observed data for all subjects (completers and subjects with early withdrawal visits) will be presented.

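### Week 156 summaries pool both randomized arms in one CZP column, so response after 3 years of CZP cannot be told apart from response after a placebo year

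*SAP*

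**What the plan says.** Entry to the extension (SFE) is open to both arms. Section 2.3.1 says that after Week 52 "subjects on double-blind study treatment may receive open-label CZP treatment for an additional 2 years", without distinguishing placebo from CZP. It adds: "Subjects who withdrew from double-blind study treatment and transitioned to open-label CZP treatment are also eligible". The Week 156 efficacy set (Section 3.5.7) is every FAS subject "who continued into the SFE Period and who received at least 1 dose of CZP in the SFE Period", whatever the arm or earlier exposure.

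Section 3.6 puts the extension's by-visit data into one column: "For the by visit data collected during the SFE period, subjects will be presented in a single CZP 200mg Q2W treatment group". It also gives extension adverse events a single open-label CZP group.

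Section 8.4 gives the purpose: "In order to assess long-term efficacy of CZP for subjects with nr-axSPA, the following summaries will be presented on the SFE-FAS". It plans subgroups by age, gender, symptom duration, HLA-B27 and MRI/CRP class, but not by randomized arm. On the reference point, Section 3.3 says: "The same Baseline definition will be used for the open-label period and SFE period". That is the last value before any double-blind drug. Section 3.3 also announces a separate SFE Baseline for some tables, which it does not name.

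Two places do not fit a single column. Section 4.2.3 defines the Week 156 non-responder denominator per treatment group. Sections 3.6 and 11.1 split adverse events and exposure by double-blind arm for the earlier open-label CZP period.

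**The concern.** One label, CZP 200mg Q2W, names the randomized arm up to Week 52 and then a different set of subjects at Week 156. A reader who compares the Week 52 CZP rate with the Week 156 CZP rate is comparing different people, so maintenance of response cannot be read from the two figures.

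Response is also measured from Week 0. A placebo subject who met ASDAS-MI at Week 52 and still meets it at Week 156 counts as a responder in the CZP column, although the response came before any CZP. Placebo subjects still on double-blind treatment at Week 52 are probably a selected group, because Section 8.1.3.2 lets investigators discontinue subjects who are not responding.

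For safety the point is smaller: the extension's adverse event column mixes placebo completers in their first CZP exposure with subjects in their third year.

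**Working it through.** **Inputs from the SAP.** Section 2.4: 150 per arm; ASDAS-MI at Week 52 expected at 40% (CZP) and 20% (placebo); 2-sided 0.05; power 95%. Section 8.1: a Week 52 responder must still be on double-blind treatment. Section 2.3.1: "The last dosing visits will be at Week 154", and "Eligible subjects are allowed to roll-over to the SFE-period up to 3 months after completion of the Week 52 assessments". The SAP gives no SFE-FAS size, placebo-origin share or expected Week 156 rate, so those values below are assumptions.

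**1. The plan's own figure.** The standard error is √(2 × 0.3 × 0.7 / 150) = 0.0529 under the null and √((0.24 + 0.16) / 150) = 0.0516 under the alternative. Power = Φ((0.20 − 1.96 × 0.0529) / 0.0516) = 96.9%, or 95.9% with continuity correction. The stated 95% is reproduced. It concerns Week 52 and is not affected by this point.

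**2. Response before any CZP.** CZP: 0.40 × 150 = 60. Placebo: 0.20 × 150 = 30. Placebo share of Week 52 responders: 30 / 90 = 33%.

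**3. CZP duration under one label** (last dose plus a 2-week dosing interval).
- Randomized to CZP: 154 + 2 = 156 weeks, 3.0 years.
- Placebo completers: 154 − 52 + 2 = 104 weeks, 2.0 years.
- Placebo completers starting 3 months (13 weeks) late, if Week 154 is kept: 91 weeks, 1.75 years.
- Placebo subjects who switched to open-label CZP before Week 52: between 2 and 3 years.

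**4. Gap between the pooled and CZP-randomized rates.** With w the placebo-origin share, pooled rate = p(CZP) + w × [p(placebo-origin) − p(CZP)]. The gap is w times the rate difference.
- Smallest case: 0.20 × 10 = 2 points.
- Largest case: 0.50 × 20 = 10 points.

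The sign follows the sign of the rate difference, which is unknown.

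**5. Direction.** Suppose that exactly the 90 expected Week 52 responders enter and keep their response and nobody else responds. This is an extreme case, used only for the sign.
- SFE-FAS 270, equal split: CZP-randomized 60/135 = 44.4%; pooled 90/270 = 33.3%. Pooling lowers the rate.
- SFE-FAS 180, equal split: 60/90 = 66.7%; pooled 90/180 = 50.0%. Pooling lowers it.
- SFE-FAS 180, 20% placebo-origin (36 subjects): 60/144 = 41.7%; pooled 90/180 = 50.0%. Pooling raises it.

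Pooling raises the rate when 90/N > 60/[N(1 − w)], that is, when w < 1/3.

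**6. Precision cost of a split** (95% Clopper-Pearson, 40% response assumed).
- Pooled n = 200: 33.2-47.1%; n = 100 per arm: 30.3-50.3%.
- Pooled n = 300: 34.4-45.8%; n = 150 per arm: 32.1-48.3%.

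**The case against.** The strongest reply is that Section 8.4 sets only a general descriptive aim. It names no 3-year duration, no maintenance estimand and no comparison between arms. A placebo completer seen at Week 156 has had about 2 years of CZP, which is long-term by any ordinary reading. These are other efficacy variables, outside the testing hierarchy and without tests. All of this stands. A reader might infer that the extension cannot answer its long-term efficacy question, but the SAP does not support that.

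A reader might also infer that the 30 placebo responders inflate the Week 156 rate by 30/270 = 11 to 30/180 = 17 points. They do not. That figure is their share of the numerator over an assumed denominator. It ignores the other placebo-origin subjects in the denominator and needs complete roll-over and complete retention of response. Step 5 of the working shows that pooling can lower the rate on the same assumptions.

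On safety, first-exposure events do not rest on the extension column alone. The double-blind CZP arm gives 52 weeks of placebo-controlled first exposure, placebo subjects who switched early have their own column, and exposure-adjusted rates are planned.

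Some by-arm information already exists: Section 5.1 gives extension entry and completion by treatment group, and Section 3.1 sorts listings by treatment group. Table shells, which are not shown, may fix the columns. None of this puts the Week 156 results by arm into the plan's text, and Section 3.6 says the opposite.

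**Conclusion.** The point holds as a limit on what the planned displays can show. The single column combines about 2 and about 3 years of CZP and includes subjects expected to have responded before any CZP (30 of 90 Week 52 responders, if the planning rates hold). It cannot separate 3-year CZP response or its maintenance from response after a placebo year. The SFE Baseline helps only in part, because the tables that use it are not named and no split by arm accompanies it.

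The direction of the gap from the CZP-randomized rate is undetermined. Its size is about 2 to 10 points for an assumed placebo-origin share of 20-50% and an assumed rate difference of 10-20 points. The Week 52 primary analysis, its power and the testing hierarchy are untouched. This is a cheap and worthwhile improvement in presentation, not a failure of the extension.

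**What to change.** - Keep the pooled column. Add columns by randomized arm (CZP->SFE and PBO->SFE) to the Section 8.4 tables and to the extension adverse event summaries, as Section 3.6 already does for open-label CZP adverse events.
- For placebo-origin subjects, also show change from SFE Baseline, or Week 156 response by Week 52 responder status. Identify early switchers in a footnote, because their SFE Baseline already follows CZP.
- Name in Section 3.3 the tables that use the SFE Baseline.
- Reconcile the single group in Section 3.6 with the per-treatment-group denominator in Section 4.2.3.

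A finer split by full CZP history in every table is not needed, nor is restricting the efficacy statement to CZP-randomized subjects. Randomized arm is recorded for every subject, and Section 4.3 releases treatment codes to the reporting team at the Week 52 lock, so no new data are required. The cost is smaller denominators and wider exact intervals per column, as in step 6 of the working.
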